##### Treatment Period

At all visits after the Screening Period, MBW tests should be performed pre-bronchodilator. Each MBW will be performed in multiple replicates at each visit according to the MBW manual.

LCI will be derived from MBW testing. LCI2.5 represents the number of lung turnovers required to reduce the end tidal inert gas concentration to 1/40th of its starting value, [REDACTED]

[figure not shown]
The mean LCI value at each visit will be calculated using all technically acceptable replicates. All LCI replicate values will be provided by a central reader; however, the LCI central reader will not perform the calculation for the mean LCI values at visits. The mean LCI value at each Treatment Period Visit will be calculated by the sponsor or sponsor designee from the technically acceptable values provided by the LCI central reader.

[figure not shown]
Detailed MBW procedures will be supplied in the Study Reference Manual.

**11.4.4 Weight, Stature, and BMI**

See Section [11.5.4](#).

**11.5 Safety**

Safety evaluations will include AEs, clinical laboratory assessments, clinical evaluation of vital signs, physical examinations (PEs), and OEs.

### 11.5.1 Adverse Events

All AEs will be assessed, documented, and reported in accordance with ICH GCP guidelines. Section 13.1 outlines the definitions, collection periods, criteria, and procedures for documenting, grading, and reporting AEs. A separate document that details AE CRF completion guidelines for investigators as well as training will be provided.

### 11.5.2 Clinical Laboratory Assessments

The safety laboratory test panels are shown in Table 11-1 and will be performed as indicated in Table 3-2. The timing of clinical laboratory assessments is described in Section 11.1. Additional clinical laboratory evaluations will be performed at other times if judged to be clinically appropriate. Laboratory test results that are abnormal and considered clinically significant will be reported as AEs (see Section 13.1).

**Table 11-1 Safety Laboratory Test Panels**

Serum Chemistry	Hematology
Glucose	Hemoglobin
Blood urea nitrogen	Erythrocytes:
Creatinine	Mean corpuscular hemoglobin
Sodium	Mean corpuscular hemoglobin concentration
Potassium	Mean corpuscular volume
Calcium	Platelets
Chloride	Reticulocytes (absolute)
Magnesium	Leukocytes
Bicarbonate	Differential (absolute and percent):
Inorganic phosphate	Eosinophils
Total bilirubin, direct bilirubin	Basophils
Alkaline phosphatase	Neutrophils
Aspartate aminotransferase	Lymphocytes
Alanine aminotransferase	Monocytes
Lactate dehydrogenase	
Gamma glutamyl transferase	
Total protein	
Albumin	
Creatine kinase	
Amylase	
Lipase	

Clinical laboratory assessments from screening will have no clinically significant findings that preclude participation in the study, as judged by the investigator, for a subject to receive study drug on Day 1.

**CF genotype (Screening Period only):** Subjects without a documented genotype in their medical record will be tested to assess *CFTR* genotype.

For purposes of study conduct and data analysis, samples will be analyzed at a central laboratory. However, at the discretion of the local investigator, samples may be analyzed at a local laboratory for management of urgent medical issues, including if a subject cannot return to the clinical study site for the mandatory liver function testing (Section 11.5.3). If a local laboratory

test value is found to be abnormal and clinically significant, it will be verified by the central laboratory as soon as possible after the investigator becomes aware of the abnormal result. If it is not possible to send a specimen to the central laboratory (e.g., the subject was hospitalized elsewhere) ideally within 48 to 72 hours, the investigator may base the assessment of an AE on the local laboratory value.

### 11.5.3 Elevation of Liver Function Test Parameters

#### Mandatory Liver Function Testing

Liver function testing (ALT, AST, gamma-glutamyl transferase [GGT], alkaline phosphatase [ALP], and total bilirubin) must be performed while subjects are receiving study drug treatment (see Table 3-2 and Section 11.5.2). These blood samples should be processed and shipped immediately per the Laboratory Manual.

Subjects with new ALT or AST elevations of  $\geq 3 \times \text{ULN}$  and clinical symptoms will be followed closely, including repeat confirmatory testing performed by the central laboratory within 48 to 72 hours of the initial finding and subsequent close monitoring of ALT and AST levels, as clinically indicated. If a subject cannot return to the site for liver function testing, a local laboratory may be used. Elevations in LFTs (ALT or AST  $\geq 3 \times \text{ULN}$ ) at the local laboratory must be reported immediately to the medical monitor AND the subject must have the tests repeated and sent to the central laboratory as soon as possible (ideally within 48 to 72 hours).

#### Study Drug Interruption

Study drug administration **must be interrupted** immediately, and the Vertex medical monitor or designee must be notified, if any of the following criteria is met:

- ALT or AST  $\geq 8 \times \text{ULN}$
- ALT or AST  $\geq 5 \times \text{ULN}$  for more than 2 weeks
- ALT or AST  $\geq 3 \times \text{ULN}$  in association with total bilirubin  $\geq 2 \times \text{ULN}$  and/or clinical jaundice

A thorough investigation of potential causes should be conducted, and the subject should be followed closely for clinical progression.

#### Resumption of Study Drug

If a convincing alternative etiology is identified for the LFTs (ALT, AST, and total bilirubin), study drug may be resumed when levels return to baseline or are  $\leq 2 \times \text{ULN}$ , whichever is higher. Approval of the Vertex medical monitor or designee is required before resumption of study drug. Upon resumption of study drug, transaminases should be assessed weekly for 4 weeks. If a protocol-defined liver test elevation occurs within 4 weeks of rechallenge with study drug, then study drug must be discontinued, regardless of the presumed etiology.

#### Discontinuation of Study Drug

If no convincing alternative etiology (e.g., acetaminophen use or viral hepatitis) for the elevated transaminases is identified, regardless of whether ALT or AST levels have improved, study drug treatment must be discontinued, after consulting with the Vertex medical monitor or authorized designee. Subjects in whom treatment is discontinued for elevated transaminases should have their transaminases monitored closely until levels normalize or return to baseline.

#### 11.5.4 Physical Examinations and Vital Signs

A PE of all body systems and vital signs assessment will be performed at screening and select study visits (see [Table 3-1](#) and [Table 3-2](#)). At other visits, symptom-directed PEs and symptom-directed vital sign assessments can be performed at the discretion of the investigator or healthcare provider.

A PE includes a review of the following systems: head/neck/thyroid; eyes/ears/nose/throat (EENT); respiratory; cardiovascular; lymph nodes; abdomen; skin; musculoskeletal; and neurological. Anorectal, and genital examinations will be performed when medically indicated. After screening, any clinically significant abnormal findings in PEs will be reported as AEs.

The abbreviated PE will include an assessment of the following body systems: head/neck/thyroid, EENT, cardiovascular system, respiratory system, skin, and abdomen.

Vital signs include blood pressure (systolic and diastolic), temperature (any clinically acceptable method may be used [e.g., oral or axillary]; however, the same method should be used at each visit), pulse rate, and respiration rate. The subject should rest for at least 5 minutes before having vital signs measured; additional instructions will be included in a separate Study Reference Manual.

Weight and stature will be assessed and BMI will be derived. If subjects can stand unassisted and follow directions, stature should be measured as height; otherwise, stature will be measured as length. Stature and weight must be measured with shoes off and while wearing light clothing. BMI will be calculated using the following equation:

$$\text{BMI (kg/m}^2\text{)} = \text{body weight (kg)} \div \text{stature}^2 \text{ (m}^2\text{)}$$

#### 11.5.5 Ophthalmologic Examination

Ophthalmologic examinations will be performed by a licensed ophthalmologist or optometrist.

The OE includes

- measurement of best corrected distance visual acuity of each eye; and
- pharmacologically dilated examination of the lens with a slit lamp.

If a cataract is identified and determined to be clinically significant by the ophthalmologist or optometrist, the subject's caregiver and the Vertex medical monitor will be notified.

#### 11.5.6 Contraception and Pregnancy

Not applicable.

## 12 STATISTICAL AND ANALYTICAL PLANS

This section presents a summary of the planned analyses for this protocol. Statistical analysis details for the interim analysis and the final analysis will be provided in the study statistical analysis plan (SAP), which will be finalized before the clinical data lock for the study and treatment unblinding. Details of analysis for the IDMC will be described in a separate IDMC SAP.

## 12.1 Sample Size and Power

There is limited information on the primary endpoint of MRI global chest score in this specific patient population. Only a small cohort of 17 patients similar to the patient population in this study, from Heidelberg, Germany, has some relevant information on this perspective. A vague normal prior distribution with a mean of 3.0 and an SD of 1000.0 for the mean change of MRI global chest score from baseline to the end of Year 1 in the placebo arm is used for the Bayesian sample size consideration.

The proposed sample size of 50 subjects (2:1 randomization: 33 LUM/IVA subjects and 17 placebo subjects after adjusting for a dropout rate of 10%) is also based on the number of potential subjects expected to be available for participation.

To illustrate potential outcomes, the Bayesian posterior probability that the mean change in the primary endpoint is better in the LUM/IVA group than placebo will be calculated.

For this study, a positive mean change of 3.0 points in the placebo arm (consistent with Heidelberg data) and a common SD of 5.0 in each arm were assumed. In this scenario, a maximum observed positive mean change of approximately 1.66 in the LUM/IVA arm would yield 80% Bayesian posterior probability of LUM/IVA being superior to placebo.

The actual Bayesian posterior probability of LUM/IVA being superior to placebo will be calculated using the actual observed mean change in the LUM/IVA arm and placebo arm at Week 48, which will serve as the primary analysis for this study. The primary endpoint and all secondary [REDACTED] endpoints specified in the protocol will also be analyzed using descriptive summary statistics. The reason for using descriptive summary statistics is due to the limited sample size and the associated insufficient power from the traditional statistical analysis perspective.

## 12.2 Analysis Sets

Assignment of subjects to analysis sets will be done before the clinical data lock for the study.

The **All Subjects Set** is defined as all subjects who have been randomized or have received at least 1 dose of study drug. This analysis set will be used in subject listings and a disposition summary table, unless otherwise specified.

The **Full Analysis Set (FAS)** is defined as all randomized subjects who have received at least 1 dose of study drug. The FAS will be used in efficacy analyses in which subjects will be analyzed according to their randomized treatment group.

The **Safety Set** is defined as all subjects who received at least 1 dose of study drug. The Safety Set will be used for all safety and tolerability analyses, in which subjects will be analyzed according to the treatment they received.

## 12.3 Statistical Analysis

The primary objective of this study is to explore the impact of LUM/IVA combination therapy on disease progression in subjects aged 2 through 5 years with CF, homozygous for *F508del*. The secondary objective is to explore the efficacy of LUM/IVA combination therapy in subjects aged 2 through 5 years with CF, homozygous for *F508del*.

This section presents a summary of the planned statistical analyses of efficacy and safety. The Vertex Biometrics department or a designated CRO will analyze the data derived from this

study. SAS® Version 9.2 or higher will be used to generate all statistical outputs (tables, figures, listings, and data sets).

Statistical analysis and presentation details will be provided in the SAP for the study.

### 12.3.1 General Considerations

All individual subject data for all randomized subjects exposed to study drug will be presented in data listings.

**Continuous variables** will be summarized using the following descriptive summary statistics: the number of subjects (n), mean, SD, median, minimum value, and maximum value. The precision of the measurement for each continuous variable will be specified in the SAP.

**Categorical variables** will be summarized using counts and percentages. Percentages will be presented to 1 decimal place.

**Baseline value**, unless otherwise specified, will be defined as the most recent non-missing measurement (scheduled or unscheduled) collected before the initial administration of study drug. [REDACTED]

**Change (absolute change) from baseline** will be calculated as post-baseline value - baseline value. [REDACTED]

**Relative change from baseline** will be calculated as (post-baseline value - baseline value)/baseline value. [REDACTED]

**The Treatment-emergent (TE) Period** will include the time from the first dose to the Safety Follow-up Visit or 14 days after the last dose of the study drug for subjects who do not have a Safety Follow-up Visit. [REDACTED]

### 12.3.2 Background Characteristics

Subject disposition, demographic and baseline characteristics, prior and concomitant medications, study drug exposure and compliance, and other background characteristics will be summarized. Additionally, all subject data will be presented in subject data listings. All summaries will be based on the FAS unless otherwise specified in the SAP for the study. No statistical hypothesis testing will be performed.

#### 12.3.2.1 Subject Disposition

The number and percentage of subjects in the following categories will be summarized as appropriate:

- All Subjects Set
- Randomized
- Dosed (Safety Set)
- Randomized, dosed, and carry the intended *CFTR* mutation (FAS)

- Completed study drug treatment
- Prematurely discontinued the study during the Treatment Period and the reasons for discontinuation
- Completed study/Safety Follow-up Visit
- Prematurely discontinued the study and the reasons for discontinuation

#### 12.3.2.2 Demographics, Medical History, and Baseline Characteristics

Demographics, medical history, and baseline characteristics will be summarized.

The following demographics and baseline characteristics will be summarized by initial dose group for the FAS: sex, race, ethnicity, age, weight, stature, region, baseline LCI2.5, [REDACTED] baseline MRI global chest test score, [REDACTED]

#### 12.3.2.3 Prior and Concomitant Medications

Medications used in this study will be coded by using a World Health Organization-Drug Dictionary and categorized as the following:

- **Prior medication:** any medication that started before initial dosing of study drug, regardless of when it ended
- **Concomitant medication:** medication continued or newly received at or after initial dosing of study drug through the end of the TE Period
- **Post-treatment medication:** medication continued or newly received beyond the TE Period

A given medication can be classified as a prior medication, a concomitant medication, or a post-treatment medication; both prior and concomitant; both concomitant and post-treatment; or prior, concomitant, and post-treatment. If a medication has a missing or partial missing start/end date or time and cannot be determined whether it was taken before initial dosing, concomitantly, or beyond the TE Period, it will be considered as prior, concomitant, and post-treatment.

Prior medications and concomitant medications will be summarized descriptively based on the FAS. Post-treatment medications will be listed for each subject.

#### 12.3.2.4 Study Drug Exposure and Compliance

Exposure to study drug (i.e., duration of treatment) will be summarized for the FAS in terms of duration of treatment a subject received (in days), defined as the last day minus the first day of study drug plus 1.

Dosing compliance will be summarized for the FAS and is calculated as the actual number of dosing occasions at which study drug was taken (including when administered at study visits), as a percentage of the planned number of dosing occasions.

Duration of treatment and dosing compliance will be summarized by means of descriptive summary statistics.

### 12.3.2.5 Important Protocol Deviations

An important protocol deviation (IPD) is a deviation that may significantly affect the completeness, accuracy, or reliability of the study data or that may significantly affect a subject's rights, safety, or well-being. Protocol deviations will be reviewed throughout the study. The rules for identifying an IPD will be described in the SAP.

All IPDs will be provided in an individual subject data listing, and summarized, as appropriate.

### 12.3.3 Efficacy Analysis

All efficacy analyses described in this section will be based on the FAS, unless specified otherwise. The analysis will include all available measurements through the last scheduled on-treatment visit, including measurements after treatment discontinuation.

#### 12.3.3.1 Primary Analysis for the Study

The actual Bayesian posterior probability of LUM/IVA being superior to placebo will be calculated using the actual observed mean change in the LUM/IVA arm and placebo arm at Week 48, which will serve as the primary analysis for the study.

The primary endpoint and all secondary [REDACTED] specified in the protocol will also be analyzed using descriptive summary statistics. The reason for using descriptive summary statistics is due to the limited sample size and the associated insufficient power from the traditional statistical analysis's perspective.

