**Table 3-2 Study VX16-809-121: Treatment Period and Safety Follow-up Visit**

Event/Assessment a	Treatment Period									ETT Visit b	Safety Follow-up Visit c
	Part 1: Placebo-controlled Period				Part 1/ Part 2 d	Part 2: Open-label Period e					
	Day 1	Day 3 (± 1 Day)	Day 15 (± 3 Days)	Weeks 12, 24, 36 (± 7 Days)	Week 48 (± 7 Days)	Day 338 f (± 1 Day)	Day 350 (± 3 Days)	Weeks 60, 72, 84 (± 7 Days)	Week 96 (± 7 Days)		
Abbreviated PE	X p				X p						
Serum chemistry q,r	X		X	X	X		X	X	X	X	X
Hematology q,r				X	X			X	X	X	X
MBW v	X			X	X			X	X	X	X
MRI	X w				X w,x				X w,w	X	

p An abbreviated PE will be performed 4 hours (± 30 minutes) postdose on Day 1 and at Week 48 (Section 11.5.4).

q Refer to Section 11.5.2 for details.

r If the MRI occurs before the scheduled study visit, this assessment may occur on the same day as the MRI assessment. Blood draws performed on the same day as the MRI assessment must be collected before administration of any medications related to MRI procedures.

v The MBW assessment should be performed pre-bronchodilator and before dosing. The assessment will be performed in multiple replicates. Refer to Section 11.4.2 for details.

w Subjects may complete the imaging assessment up to 7 days before the scheduled visit. Screening assessments must be completed, inclusion and exclusion criteria must be reviewed, and subjects must meet eligibility criteria relevant at the time before participating in the baseline MRI assessment up to 7 days before Day 1. If the MRI is performed before the scheduled visit, the blood draws for serum chemistry, hematology, and ██████████ may be performed on the day of the MRI assessment. Blood draws for any assessment performed on the same day as MRI testing must be collected before administration of any medications related to MRI procedures. ██████████

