## **9.2 Method of Assigning Subjects to Treatment Groups**

### **Part 1**

An interactive web or voice response system (IXRS) will be used to assign subjects to treatment. The randomization code will be produced by Vertex Biostatistics or a qualified randomization vendor. The Vertex study biostatistician will review and approve the production of the final randomization list, which will be reviewed and approved by a designated unblinded biostatistician who is not a member of the study execution team (SET).

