3 INTRODUCTION

This statistical analysis plan (SAP) for the Part 1 (interim) and final analysis is based on the most recent approved clinical study protocol (CSP), electronic case report form (eCRF), and eCRF completion guidelines.

This SAP (Methods) documents the planned statistical analyses of efficacy and safety endpoints for the Part 1 analysis and the final analysis (FA), which have been pre-defined in the VX16-809-121 study protocol. It also documents analyses for [REDACTED] safety variables not specified in the protocol, which will provide supportive information for the scientific understanding of the drug entity.

The Vertex Biometrics Department will perform the statistical analysis of the efficacy and safety data; SAS (Version 9.4 or higher) will be used to generate all statistical outputs (tables, figures, listings, and datasets). The SAP will be finalized and approved prior to the Part 1 analysis data-cut and treatment unblinding for the Part 1 analysis. Any revisions to the approved SAP will be documented and approved in an amendment to the SAP prior to the clinical database lock for the final analysis. Any changes made to the SAP (Methods) after the clinical database lock has occurred will be documented in the clinical study report for this study.

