6.3 Randomization

Study Part 1

The proposed sample size of 50 subjects will be randomized by 2:1 ratio to the LUM/IVA arm or placebo arm.

An interactive web or voice response system (IXRS) will be used to assign subjects to treatment or placebo. The randomization code will be produced by Vertex Biostatistics or a qualified randomization vendor.

Study Part 2

Part 2 is an open-label extension period. Randomization is not applicable.

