9.2.1.2 Demographics and Baseline Characteristics

Demographics and baseline characteristics at study baseline will be summarized based on the FAS and presented by treatment group and overall.

Demographic data will include the following:

- Age at baseline (in years)
- Age group at baseline (<3 and ≥ 3 years)
- Sex (female and male)
- Ethnicity (Hispanic or Latino, not Hispanic or Latino, and not collected per local regulations)
- Race (White, Black or African American, Asian, American Indian or Alaska Native, Native Hawaiian or Other Pacific Islander, and not collected per local regulations)

[figure not shown]
Baseline characteristics will include the following:

- Weight (kg)
- Weight group (<14 kg and ≥ 14 kg)
- Weight-for-age z-score
- Stature (cm)
- Stature-for-age z-score
- BMI (kg/m^2)
- BMI-for-age z-score

Disease characteristics will include the following:

- $\text{LCI}_{2.5}$ at baseline

- 
- MRI global chest score at baseline
- 

In addition, data listings will also be provided for:

- Informed consent;
- Inclusion/Exclusion criteria violation for subjects with any such violations.

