9.2.2.1.2 Primary Analysis

The primary analysis will be performed using Bayesian methods. Specifically, the actual Bayesian posterior probability of LUM/IVA being superior to Placebo in the MRI global chest score at Week 48 will be calculated using a vague normal prior distribution. Bayesian summary statistics including the Bayesian posterior mean difference and corresponding 95% credible intervals will also be provided.

In addition, descriptive summary statistics for both between treatment arm difference and within-treatment change at Week 48 will be presented. Descriptive summary statistics including number of subjects (n), mean, median, SD, minimum, and maximum, along with the corresponding 95% CIs will be provided.

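### The primary Bayesian comparison of MRI change does not adjust for baseline MRI score; that one covariate could cut its variance by about 8–23% (assuming a baseline–Week 48 correlation of 0.5–0.8 and equal SDs)

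*Protocol*

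**What the plan says.** Protocol 12.3.3.1 makes the posterior probability of superiority the primary analysis and says that it "will be calculated using the actual observed mean change in the LUM/IVA arm and placebo arm at Week 48". Protocol 12.1 describes the same calculation. SAP 9.2.2.1.2 says that the probability "will be calculated using a vague normal prior distribution" and adds a posterior mean difference and a 95% credible interval. It states no likelihood and no covariate, and that section shows no redaction.

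Baseline MRI is part of the schedule: under Protocol Table 3-2 children must have met the relevant eligibility criteria "before participating in the baseline MRI assessment up to 7 days before Day 1". SAP 9.2.1.2 lists "MRI global chest score at baseline" among the disease characteristics to be tabulated by arm.

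On allocation, Protocol 9.2 says "An interactive web or voice response system (IXRS) will be used to assign subjects to treatment" and SAP 6.3 says "The proposed sample size of 50 subjects will be randomized by 2:1 ratio to the LUM/IVA arm or placebo arm". Neither names a stratification factor.

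**The concern.** A change score uses the baseline value, but it fixes the baseline coefficient at 1. It does not estimate how change depends on where the child started, and there is reason to expect some dependence. SAP 9.2.2.1.1 sums seven parameters graded 0 to 2 over six lobes, so a child near zero has almost no room to improve. Semi-quantitative reading also invites regression to the mean.

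No visible design feature balances baseline MRI score between arms. SAP 6.2 says that the sample size follows from the number of available children, and Protocol 12.3.3.1 concedes limited size and insufficient power. Baseline adjustment is one of the few ways to gain precision without more children or more data. At stake are the width of the credible interval and the stability of the posterior probability. No success threshold is set, so this is not a matter of a wrong decision, and there is no bias.

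**Working it through.** **Inputs from the documents.** Protocol 12.1 gives a placebo mean change of 3.0, says "a common SD of 5.0 in each arm were assumed", and gives 33 vs 17 children with 10% dropout. I take about 30 vs 15 completers (n = 45).

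**Assumed inputs.** The documents do not give the baseline–Week 48 correlation ρ or the SD ratio L = SD at Week 48 ÷ SD at baseline. I show ρ from 0.5 to 0.95, with L = 1 as the base case.

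**Step 1: reproduce the plan's own figure.** With a vague prior, the LUM/IVA mean change that gives 80% posterior probability is 3.0 − 0.8416 × SE.

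- 30 vs 15: SE = 5 × √(1/30 + 1/15) = 1.581, so the threshold is 3.0 − 1.33 = 1.67 (1.656 with a t distribution on 43 df). The protocol says approximately 1.66.
- 33 vs 17: SE = 1.493 and the threshold is 1.74.

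The protocol's figure therefore matches an unadjusted comparison of about 30 vs 15.

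**Step 2: variance ratio, adjusted to unadjusted.** Let s be the baseline SD. The variance of change is s²(1 + L² − 2ρL) = 25, so s = 5/√(1 + L² − 2ρL). The residual variance after adjustment is L²s²(1 − ρ²). The large-sample ratio is L²s²(1 − ρ²)/25, which is (1 + ρ)/2 when L = 1. Estimating the slope multiplies this by 1 + 1/(45 − 4) = 1.024.

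Results for L = 1:

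| ρ | Large-sample ratio | Ratio at n = 45 | Equivalent extra children | 95% half-width (unadjusted 1.96 × 1.581 = 3.10) |
|---|---|---|---|---|
| 0.5 | 0.75 | 0.768 | about 30% | 2.72 |
| 0.7 | 0.85 | 0.871 | about 15% | 2.89 |
| 0.8 | 0.90 | 0.922 | about 8% | 2.98 |
| 0.95 | 0.975 | 0.999 | about 0% | 3.10 |

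Extra children is 1/ratio − 1. Simulation of 30 vs 15 gave variance reductions of 22.9% at ρ = 0.5 and 8.3% at ρ = 0.8, in agreement with the table. The adjusted SE is 1.386 at ρ = 0.5 and 1.518 at ρ = 0.8, so the 80% threshold moves from 1.67 to 1.83 or 1.72.

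**Step 3: effect of chance imbalance on the unadjusted posterior.** The slope of change on baseline is ρL − 1. A baseline difference of one SE between arms, s × √(1/30 + 1/15) = 0.3162s, shifts the difference in mean change by |ρL − 1| × 0.3162s. With L = 1 this is 0.79, 0.61, 0.50 and 0.25 points at ρ = 0.5, 0.7, 0.8 and 0.95. Take a difference of 3.0 − 1.66 = 1.34 points, which gives about 80% with balanced arms.

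- Adverse imbalance (LUM/IVA starting lower): Φ((1.34 − shift)/1.581) = 64%, 68%, 70%, 75%.
- Favourable imbalance: Φ((1.34 + shift)/1.581) = 91%, 89%, 88%, 84%.

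**Step 4: sensitivity to equal SDs (n = 45).**

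- L = 1.25: ratios 0.915, 1.005 and 1.024 at ρ = 0.5, 0.7 and 0.8. The adverse posterior is 70%, 76% and 80%.
- L = 1.2: from a 10.8% reduction at ρ = 0.5 to a 2.1% loss at ρ = 0.8.
- L = 0.9: a reduction of 31.6% at ρ = 0.5 and 19.3% at ρ = 0.8.

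The large-sample gain is zero when ρL = 1, because change is then unrelated to baseline. What remains is the cost of the estimated slope, 1/41 = 2.4%.

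**The case against.** The strongest reply is that this is a choice between two valid analyses. The study is exploratory, the change score already uses baseline, the unadjusted SE already includes chance imbalance, and no threshold depends on the result. All of that stands. It limits the point to precision and robustness.

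It is also true that the 8–23% rests on a correlation and an SD ratio that the documents do not give. From the documents alone the effect could run from a slight loss to a larger gain, as Step 4 shows. The threshold moves by only 0.05 to 0.16 points. The 64% and 91% figures show how far the unadjusted posterior can swing under an imbalance; they are not the gain in a balanced trial. At the same 1.34-point difference and ρ = 0.5, the adjusted posterior would be Φ(1.34/1.386), about 83%.

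The 2.4% ceiling on cost assumes one common slope. A simulation with strongly opposed slopes in the two arms gave a loss of about 9%.

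Two textual arguments carry less weight. SAP 9.2.2.1.2 is silent on covariates, not explicitly unadjusted, but read with Protocol 12.3.3.1 it means observed means. ANCOVA, LS and MMRM in the protocol's abbreviations, and a small-sample mixed-model reference in the SAP, suggest that adjusted models may sit in redacted sections. Nothing visible applies them to the primary analysis.

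**Conclusion.** The concern holds. The primary posterior is built from unadjusted mean changes, although the most obvious prognostic covariate is already collected. The loss is one of efficiency, not validity: about 8–23% of the variance of the treatment difference at n = 45, given equal SDs and a correlation of 0.5 to 0.8. The benefit shrinks to nothing at a correlation near 0.95, or at 0.7 to 0.8 if the SD is 25% wider at Week 48. It is larger if the SD narrows. Because the expected cost is small under a common slope, the change should be made, but the trial does not fail without it.

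**What to change.** Make the change within the SAP's own deadline: "The SAP will be finalized and approved prior to the Part 1 analysis data-cut and treatment unblinding for the Part 1 analysis". In SAP 9.2.2.1.2, prespecify:

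> The primary posterior will come from a Bayesian normal linear regression of Week 48 change in MRI global chest score on treatment group and study-baseline MRI global chest score, with vague priors on the coefficients and residual variance. The posterior probability that LUM/IVA is superior, the adjusted mean difference and its 95% credible interval will be reported. The posterior from unadjusted mean changes will be reported as supportive.

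Align Protocol 12.3.3.1 with this. If the protocol is not amended, record the change and its reason explicitly in the SAP, so that it is clear which analysis is primary.

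The cost is one covariate and one degree of freedom, with no extra visits or data. The expected variance loss is about 2.4% if baseline proves unrelated to change, and somewhat more only if the arms' slopes are strongly opposed. The protocol's raw-mean result, and its link to the 1.66 illustration, survive in the supportive analysis.
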